2 TRIAL DESIGN

2.1 Trial Design

This is a multicenter, worldwide, open-label, nonrandomized, Phase 1b study of MK-8353 in combination with pembrolizumab in subjects with advanced solid tumors with a focus on subjects with \geq second line advanced non-MSI-H/dMMR colorectal cancer (CRC).

This study will evaluate the safety, tolerability, and preliminary efficacy of MK-8353 when administered in combination with pembrolizumab. There are 2 parts in this study, dose escalation and confirmation (Part 1) and cohort expansion (Part 2).

For each subject, RAS/RAF mutations and proficient versus deficient mismatch repair (pMMR vs. dMMR) status will be required for enrolling in the study. Archived tumor samples or newly obtained biopsies will be obtained during the screening period for assessment of these mutations and for biomarker evaluation.

In Part 1, the modified toxicity probability interval (mTPI) design [1] will be used to identify and confirm the recommended Phase 2 dose(s) (RP2D[s]) of MK-8353 in combination with a fixed dose of pembrolizumab in subjects with advanced malignancies. Subjects will be enrolled in 1 of 2 arms to receive MK-8353 in combination with pembrolizumab at a fixed dose of 200 mg, during 21-day cycles for approximately 24 months of treatment. In Arm A and Arm B, MK-8353 will be administered continuously at a starting dose of 50 mg twice daily (bid), or 50 mg once daily (qd), respectively (refer to Section 4.2.2). Enrollment will alternate between arms.

Initially, the protocol started at a dose of 350 mg bid of MK-8353 in combination with pembrolizumab and several dose levels for escalation from this initial dose were planned; however, 3 of the 4 subjects who received MK-8353 at 350 mg bid developed a Grade 3 rash and MK-8353 was discontinued at this dose for these 4 subjects (refer to Section 4.1.3.1).

The protocol was then amended (Amendment 1) to restart at a lower dose (100 mg bid) of MK-8353 in combination with pembrolizumab (Arm A) with a potential de-escalation dose of 50 mg bid; several dose levels for escalation were planned. The subject enrolled at 100 mg bid of MK-8353 in combination with pembrolizumab developed several Grade 3 toxicities, including Grade 3 rash, and the next subjects were enrolled at 50 mg bid of MK-8353 in combination with pembrolizumab (refer to Section 4.1.3.1.).

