4.2.2.2 Maximum Dose/Exposure for This Trial

The maximum dose of oral MK-8353 for this trial is as follows:

Arm A: 350 mg bid; maximum 700 mg total per day

Arm B: 1200 mg qd; maximum 1200 mg total per day

Arms C and D: 600 mg qd; maximum 600 mg total per day

The maximum dose of pembrolizumab will be 200 mg administered intravenously q3w.

The maximum dose of MK-8353 is based on the single agent doses tested in the healthy volunteer study and in Protocol 001 (refer to Section 4.1.2.1). Also, preliminary data from Protocol 013 at the 350 mg bid dose of MK-8353 in combination with pembrolizumab have suggested intolerable skin toxicity (refer to Section 4.1.3.1).

The maximum dose of pembrolizumab is based on single agent doses tested in KN-001, as well as the highest doses tested in combination in Phase 1 to 2 trials (refer to Section 4.1.2.2 and package circular for KEYTRUDA).

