4.2.2.3 Rationale for Dose Interval and Trial Design

In MK-8353 Protocol 001, doses from 100 mg bid to 800 mg bid were evaluated. The highest dose level (800 mg bid) was found to be not tolerable (refer to Section 4.1.2.1 and the MK-8353 IB).

Although a dose of 350 mg bid was well tolerated in monotherapy and showed signs of clinical activity in Protocol 001, preliminary data from Protocol 013 have suggested that MK-8353 at 350 mg bid in combination with pembrolizumab leads to unacceptable toxicity (Grade 3 rash reported in 3 of the 4 subjects treated at this dose; refer to Section 4.1.3.1).

In the current amendment, dose escalation of MK-8353 (in combination with pembrolizumab) will start at 50 mg bid and 50 mg qd in Arm A and Arm B, respectively (continuous schedule). In spite of the high inter-individual variability observed in PK data from MK-8353, these doses are expected to produce meaningfully lower exposure from the previously tested 350 mg bid dose. The 2 optional Arms C and D will explore a drug holiday schedule (1 week on/1 week off; Arm C), and a 2-week run-in with MK-8353 as a single agent prior to the continuous administration of the combination (Arm D). The 2 optional arms could be triggered if unacceptable toxicities occur in Arm A and/or Arm B. In Arm B, once daily doses that achieve the same average exposure at steady state compared with bid doses (with lower trough levels, but higher C_{max}) will be explored in parallel to Arm A.

Pembrolizumab will be evaluated in the combination therapy at its full single-agent dose (200 mg intravenously q3w), and will not be escalated or de-escalated during this trial (refer

to Section 5.2.1). This dose was shown to be efficacious as a single agent and in combination, with an acceptable AE profile.

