5.2.1.2 Dose Escalation and Confirmation

In Part 1 of the study, an mTPI design [1] with a target DLT rate of approximately 30% will be applied for dose escalation and confirmation to determine a RP2D for MK-8353 in combination with pembrolizumab.

In Arms A (bid continuous) and B (qd continuous), predetermined dose levels of MK-8353 (in combination with a fixed dose of pembrolizumab) will be explored independently. In Arm A, a de-escalation dose of 50 mg is available if the starting dose of 100 mg is deemed not tolerable. All dose escalation and de-escalation decisions will be based on the occurrence of DLTs at a given dose during the DLT evaluation period and will be made jointly by the

investigators and the Sponsor. In Arm B, additional intermediate dose levels between 600 and 1200 mgs may be explored.

Additionally, the investigators and the Sponsor can decide jointly to open the 2 optional schedules (Arm C and/or Arm D) based on safety information and PK data obtained from Arms A and B. All dose escalation and de-escalation decisions in these 2 arms will be also based on the occurrence of DLTs at a given dose during the DLT evaluation period (Cycle 1 for Arm C [21 days], and Cycles 1 and 2 for Arm D [35 days]) and will be made jointly by the investigators and the Sponsor.

Additional doses of 10 mg and 30 mg could be explored in any of the 4 arms based on safety information and exposure data obtained at the higher doses. The decision to explore these lower doses will be made jointly by the investigators and the Sponsor.

The dose of pembrolizumab will remain constant at 200 mg q3w for each dose level of MK-8353 and in each arm.

In [Table 3](#), the number of subjects treated is indicated in the columns and the number of subjects who experienced a DLT is indicated in the rows. Dosing decisions include escalate to the next higher dose (E), stay at the current dose (S), de-escalate to the next lower dose (D), and de-escalate to a lower dose and never test this dose again (ie, unacceptably toxic dose; DU).

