For example, if 1/3 subjects have experienced a DLT at a given dose level, no more than an additional 3 subjects should be enrolled at this dose level until additional DLT data are available. This is because this dose level would be considered unacceptably toxic if all 3 of the additional subjects experience a DLT (ie, 4/6 subjects with DLTs as in [Table 3](#)).

This is a Phase 1b assessment of MK-8353 in humans, and the PK, PD, and safety profiles of the compound are still being elucidated. This protocol is written with some flexibility to accommodate the inherent dynamic nature of Phase 1 clinical studies. Modifications to the dose, dosing regimen and/or clinical or laboratory procedures currently outlined above may be required to achieve the scientific goals of the study objectives and/or to ensure appropriate safety monitoring of the study participants. As such, some alterations from the currently outlined dose and/or dosing regimen may be permitted based on newly available data, but the maximum daily dose may not exceed those currently outlined in the protocol, including repeat of or decrease in the dose of the study intervention administered in any given arm.

Dose escalation and confirmation will end after 14 subjects have been treated at any one of the selected doses. The pool-adjacent-violators-algorithm [1] will be used to estimate the DLT rates across doses. The dose with an estimated DLT rate closest to 30% may be treated as a preliminary MTD. The totality of the data will be considered before a dose is selected to carry forward to Part 2 and the escalation schedule may be adjusted based on PK and safety data emerging throughout the study to determine the RP2D.

Note that although 30% was the target toxicity rate used to generate the guidelines in [Table 3](#), the observed rates of subjects with DLTs at the MTD may be slightly above or below 30%.

Table 3 Dose Escalation and Confirmation Rules Based on the Modified Toxicity Probability Interval Design

Number of toxicities	Number of subjects treated at current dose											
	3	4	5	6	7	8	9	10	11	12	13	14
0	E	E	E	E	E	E	E	E	E	E	E	E
1	S	S	S	E	E	E	E	E	E	E	E	E
2	D	S	S	S	S	S	S	S	E	E	E	E
3	DU	DU	D	S	S	S	S	S	S	S	S	S
4		DU	DU	DU	D	D	S	S	S	S	S	S
5			DU	DU	DU	DU	DU	D	S	S	S	S
6				DU	DU	DU	DU	DU	DU	D	S	S
7					DU	D						
8						DU						
9							DU	DU	DU	DU	DU	DU
10								DU	DU	DU	DU	DU
11									DU	DU	DU	DU
12										DU	DU	DU
13											DU	DU
14												DU

Target toxicity rate = 30%

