All adverse events that occur after the consent form is signed but before treatment allocation/randomization must be reported by the investigator if they cause the subject to be excluded from the trial, or are the result of a protocol-specified intervention, including but not limited to washout or discontinuation of usual therapy, diet, placebo treatment or a procedure. From the time of treatment allocation/randomization through 30 days following cessation of treatment, all adverse events must be reported by the investigator. Such events will be recorded at each examination on the Adverse Event case report forms/worksheets. The reporting timeframe for adverse events meeting any serious criteria is described in section 7.2.3.1. The investigator will make every attempt to follow all subjects with non-serious adverse events for outcome.

Electronic reporting procedures can be found in the Electronic Data Capture (EDC) data entry guidelines. Paper reporting procedures can be found in the Investigator Trial File Binder (or equivalent).

Adverse events will not be collected for subjects during the pre-screening period (for determination of archival tissue status) as long as that subject has not undergone any protocol-specified procedure or intervention. If the subject requires a blood draw, fresh tumor biopsy etc., the subject is first required to provide consent to the main study and AEs will be captured according to guidelines for standard AE reporting.

7.2.1 Definition of an Overdose for This Protocol and Reporting of Overdose to the Sponsor

For this trial, an overdose of MK-8353 will be defined as any dose above what is indicated for the specific treatment arms:

Arm A: 350 mg twice a day

Arm B: 1200 mg once a day

Optional Arms C and D: 600 mg once a day

An 800 mg bid dose has been administered every day in MK-8353 Protocol 001 in 6 subjects as a single agent (refer to Section 4.1.2.1).

An overdose of pembrolizumab will be defined as any dose of 1000 mg or greater (≥ 5 times the indicated dose).

No specific information is available on the treatment of overdose of MK-8353 or pembrolizumab. In the event of overdose, the subject should be observed closely for signs of toxicity. Appropriate supportive treatment should be provided if clinically indicated.

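### The Arm A dose ceiling and overdose line (350 mg bid) lie above the top open Arm A level, at a dose where the protocol says early data suggest unacceptable toxicity

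*Combined protocol and SAP*

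**What the plan says.** **Ceiling.** Section 4.2.2.2 gives the maximum MK-8353 dose by arm. For Arm A it reads "Arm A: 350 mg bid; maximum 700 mg total per day". The same section goes on to note that early data at this dose with pembrolizumab pointed to skin toxicity that could not be tolerated.

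**Experience at that dose.** Section 4.2.2.3 says that preliminary data suggest that "MK-8353 at 350 mg bid in combination with pembrolizumab leads to unacceptable toxicity", citing Grade 3 rash in 3 of 4 subjects. Section 2.1 adds that 3 of the 4 "developed a Grade 3 rash and MK-8353 was discontinued at this dose for these 4 subjects".

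**Current ladder.** Section 4.2.2 takes Arm A from 50 mg bid up to, possibly, 300 mg bid. Section 5.2 counts six planned Arm A levels starting at 50 mg bid, which leaves out DL1 (350 mg bid). A footnote in Section 2.2 places DL1 in the past. Tables 2 and 4 nevertheless list DL1 with the other Arm A levels and do not mark it closed.

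**Flexible dosing.** Section 5.2.1.2 allows the dose or regimen to be altered on new data, including repeating a dose, with the limit that "the maximum daily dose may not exceed those currently outlined in the protocol". The same section says that for a dose marked DU the decision is to de-escalate and "never test this dose again (ie, unacceptably toxic dose; DU".

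**Overdose.** In Section 7.2.1, "an overdose of MK-8353 will be defined as any dose above what is indicated for the specific treatment arms". The Arm A entry is "Arm A: 350 mg twice a day".

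**The concern.** Two safety limits in Arm A use the 350 mg bid figure: the cap on flexible dosing and the line for overdose reporting. That figure is a dose the protocol has moved away from. A cap is useful only if it agrees with the rest of the plan on which doses are open, and here the sections give different answers for doses above 300 mg bid.

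The overdose line also decides how quickly an event is reported. Under Section 7.2.1 an adverse event resulting from an overdose is reported as serious, an overdose without effects is an event of clinical interest, and both go to the sponsor within 24 hours. An Arm A dosing error above the top planned level but not above 350 mg bid gets neither treatment. A non-serious event, or an error without symptoms, would miss the fast route.

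**Working it through.** **1. Ceiling against top open level, by arm** (ceilings from Section 4.2.2.2; levels from Section 4.2.2 and Tables 2 and 4)

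| Arm | Ceiling, mg/day | Top open level, mg/day | Ratio |
|---|---|---|---|
| A | 2 × 350 = 700 | DL6A: 2 × 300 = 600 | 700/600 = 1.17 |
| B | 1200 | DL9B: 1200 | 1.00 |
| C | 600 | DL7C: 600 | 1.00 |
| D | 600 | DL7D: 600 | 1.00 |

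Only in Arm A does the ceiling exceed the ladder. Section 5.2 still counts seven levels for Arm B where the tables list nine, so its counts are not conclusive alone. For Arm A, however, its count of six agrees with the list in Section 4.2.2, which stops at 300 mg bid.

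**2. Would Table 3 close DL1?** Inputs are the 30% target, the Beta(1,1) prior and ε1 = ε2 = 0.05, all from Table 3 and its notes. With x DLTs in n subjects the posterior is Beta(1+x, 1+n−x). The decision is the interval with the largest unit probability mass, among (0, 0.25), (0.25, 0.35) and (0.35, 1). DU applies if P(p > 0.30) exceeds a cutoff. The documents do not state the cutoff. I assumed 0.95, which reproduces every legible cell in rows 0 to 6 of Table 3.

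For 3 of 4 the posterior is Beta(4,2), with F(t) = 5t⁴ − 4t⁵:
- F(0.30) = 0.0405 − 0.00972 = 0.0308, so P(p > 0.30) = 0.969 > 0.95.
- Unit masses: E = 0.0156/0.25 = 0.06; S = 0.0384/0.10 = 0.38; D = 0.9460/0.65 = 1.46.
- Decision: **DU**, as printed in Table 3.

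Sensitivity to how many of the 4 subjects had a DLT:

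| DLTs in 4 | P(p > 0.30) | Decision |
|---|---|---|
| 1 | 0.528 | S |
| 2 | 0.837 | S |
| 3 | 0.969 | DU |
| 4 | not needed | DU (Table 3) |

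DU therefore needs at least 3 protocol-defined DLTs. Under Section 5.2.1.5 a Grade 3 rash is a DLT if it lasts more than 3 days despite optimal supportive care, or if another criterion is met, such as stopping treatment in Cycle 1 because of it. The text available to this review gives neither the duration nor the cycle. The account of DL1 in Section 4.1.3.1, to which the protocol refers, was not available.

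**3. Is 350 mg bid open or closed?**
- Pointing to open: the flexible-dosing limit read with Section 4.2.2.2; the explicit allowance for repeating a dose; DL1 listed unmarked in Tables 2 and 4.
- Pointing to closed: the ladder in Sections 4.2.2 and 5.2; the past-tense footnote in Section 2.2; the never-retest rule, if step 2 gives DU.

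**4. Overdose line.** The definition is strict (above the threshold). Arm A doses above 300 mg and up to and including 350 mg, twice a day, exceed every planned level and are not overdoses. The band is 50 mg per dose, or 100 mg/day.

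**The case against.** The strongest reply is that nobody is likely to return to 350 mg bid. Escalation decisions rest on DLTs and are made jointly by the investigators and the sponsor after safety review. The planned ladder stops short of the dose. If DL1 is DU, retesting is already forbidden. Section 4.2.2.2 can also be read as a record of the highest dose given in this trial, and it discloses the skin toxicity openly. All of this lowers the practical risk, but it does not remove the conflict: the flexible-dosing clause uses the maximum as a working limit, not as a historical record.

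A reader might go further in four ways that the documents do not support.

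- **That DL1 is formally DU.** No available section says so. The protocol's wording is that preliminary data suggest unacceptable toxicity, and 2 DLTs in 4 would give S.
- **That the plan permits re-escalation to 350 mg bid.** One clause read alone leaves it open; other text closes it. The defect is inconsistency, not permission.
- **That the mismatch allows a 7-fold dosing error** (350/50) to escape the overdose definition. That ratio comes mainly from setting thresholds by arm and not by allocated dose. A line at DL6A would still allow 300/50 = 6-fold, and the same construction allows 1200/50 = 24-fold in Arm B and 600/50 = 12-fold in Arms C and D.
- **That toxicity after such an error would be credited to the allocated dose.** Section 8.5.1 analyses subjects by the treatment actually received when there are administration errors, and Section 8.11 reports deviations from directed administration.

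**Conclusion.** The point holds as an internal contradiction about a dose limit. The Arm A ceiling is 100 mg/day (17%) above the top level the plan now offers. It sits at a dose for which the protocol itself reports discontinuation in all 4 subjects, and Arm A is the only arm with such a gap. The flexible-dosing clause and the ladder disagree on whether that dose is available. The overdose definition leaves a band of 50 mg per dose above the planned range outside 24-hour overdose reporting.

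This conclusion rests on the text and does not need the DU result. DU adds weight only if at least 3 of the 4 subjects had protocol-defined DLTs, and the computed probability also assumes the 0.95 cutoff. If the account in Section 4.1.3.1 settles the status of DL1, the other sections should be brought into line with it.

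**What to change.** Reconcile Section 4.2.2.2, the flexible-dosing paragraph in Section 5.2.1.2, Section 7.2.1, and Tables 2 and 4. In particular:

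- State the current status of DL1 and show it in both tables.
- Give one Arm A ceiling that agrees with that status and with the never-retest rule.
- Make the flexible-dosing limit and the Arm A overdose definition both refer to that single figure.

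The figure itself is for the sponsor's clinical team; none is proposed here. The cost is wording in the sections and tables named. The planned Arm A ladder, the sample size and the analyses do not change.

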4.2.2.3 Rationale for Dose Interval and Trial Design

In MK-8353 Protocol 001, doses from 100 mg bid to 800 mg bid were evaluated. The highest dose level (800 mg bid) was found to be not tolerable (refer to Section 4.1.2.1 and the MK-8353 IB).

Although a dose of 350 mg bid was well tolerated in monotherapy and showed signs of clinical activity in Protocol 001, preliminary data from Protocol 013 have suggested that MK-8353 at 350 mg bid in combination with pembrolizumab leads to unacceptable toxicity (Grade 3 rash reported in 3 of the 4 subjects treated at this dose; refer to Section 4.1.3.1).

In the current amendment, dose escalation of MK-8353 (in combination with pembrolizumab) will start at 50 mg bid and 50 mg qd in Arm A and Arm B, respectively (continuous schedule). In spite of the high inter-individual variability observed in PK data from MK-8353, these doses are expected to produce meaningfully lower exposure from the previously tested 350 mg bid dose. The 2 optional Arms C and D will explore a drug holiday schedule (1 week on/1 week off; Arm C), and a 2-week run-in with MK-8353 as a single agent prior to the continuous administration of the combination (Arm D). The 2 optional arms could be triggered if unacceptable toxicities occur in Arm A and/or Arm B. In Arm B, once daily doses that achieve the same average exposure at steady state compared with bid doses (with lower trough levels, but higher C_{max}) will be explored in parallel to Arm A.

Pembrolizumab will be evaluated in the combination therapy at its full single-agent dose (200 mg intravenously q3w), and will not be escalated or de-escalated during this trial (refer

to Section 5.2.1). This dose was shown to be efficacious as a single agent and in combination, with an acceptable AE profile.

4.2.3 Rationale for Endpoints

4.2.3.1 Efficacy Endpoints

The efficacy of MK-8353 in combination with pembrolizumab will be evaluated in subjects with advanced solid tumors, and in subjects with \geq second line advanced non-MSI-H/dMMR CRC, by measuring ORR, DCR, DOR, PFS, and OS.

Overall response rate will be used as a secondary endpoint as assessed by the investigator based on RECIST 1.1, to evaluate efficacy of MK-8353 in combination with pembrolizumab in subjects with advanced solid tumors, and in subjects with \geq second line advanced non-MSI-H/dMMR CRC.

Radiological images (eg, computed tomography [CT], magnetic resonance imaging [MRI]) will be collected for possible analysis by blinded, independent central review. The Site Imaging Manual (SIM) contains specific instructions for the acquisition and submission of radiologic images to the central imaging vendor for this study.

Exploratory endpoints include OS, DCR, DOR, and PFS as assessed by the investigator based on RECIST 1.1 (refer to Appendix 12.4).

Secondary and exploratory efficacy endpoints will also be summarized according to RAS/RAF mutant status, pMMR status, and colon side of the tumors (in subjects with non-MSI-H/dMMR CRC).

Immune-related RECIST could be used by the investigator for treatment decision as outlined in Section 7.1.2.6 and Appendix 12.5.

4.2.3.2 Safety Endpoints

The primary safety objective of this study is to characterize the safety and tolerability of MK-8353 in combination with pembrolizumab in subjects with advanced solid tumors, and in subjects with \geq second line advanced non-MSI-H/dMMR CRC.

The primary safety analysis will be based on subjects who experience toxicities as defined by NCI CTCAE version 4.0 criteria for the duration of the study. Dose-limiting toxicities will be evaluated during Cycle 1 for the purpose of dose escalation and de-escalation decisions.

Safety will be assessed by quantifying the toxicities experienced by subjects who have received MK-8353 and pembrolizumab and their grades, including SAEs and events of clinical interest (ECIs).

Safety will be assessed by reported AEs using NCI CTCAE, version 4.0. The attribution to drug, time-of-onset, duration of the event, its resolution, and any concomitant medications administered will be recorded. Safety parameters that will be analyzed include, but are not limited to, overall AEs, specific SAEs, SAEs, fatal AEs, and laboratory changes.

Other safety endpoints include laboratory safety assessments, Eastern Cooperative Oncology Group (ECOG) performance status, vital signs, and physical examinations.

